4.0 OVERVIEW OF STUDY DESIGN/INTERVENTION

This is a 2-group parallel (high-grade astrocytoma, diffuse pontine tumor), single stage study investigating cetuximab in conjunction with external beam radiation therapy, followed by cetuximab and irinotecan in pediatric and young adult patients. Optional exploratory components of the study include (1) correlation of tumor molecular markers with outcome, (2) CSF proteomics, and (3) assay of serum cytokine levels in patients who develop a cetuximab-associated rash.

5.0 THERAPEUTIC/DIAGNOSTIC AGENTS

5.1 CETUXIMAB

Cetuximab is an anti-EGFR human-to-murine chimeric antibody. Cetuximab is expressed in SP2/0 myeloma cell line, grown in large scale cell culture bioreactors and purified to a high level purity using several purification steps including protein A chromatography, ion exchange chromatography, low pH treatment and nanofiltration. Cetuximab is not known to be a vesicant.

Supplier/How Supplied: Bristol-Myers Squibb (BMS) will supply cetuximab free of charge to the patient. The product is a sterile, clear, colorless liquid of pH 7.0 to 7.4, which may contain a small amount of easily visible, white, amorphous cetuximab particulates. Each single-use 50-mL vial contains 100 mg of cetuximab at a concentration of 2 mg/mL and is formulated in a preservative-free solution containing 8.48 mg/mL sodium chloride, 1.88 mg/mL sodium phosphate dibasic heptahydrate, 0.42mg/mL sodium phosphate monobasic monohydrate, and water for injection, USP.

Packaging and Labeling: Cetuximab for injection will be supplied by BMS in single-use, readyto-use 50-mL vials containing 2 mg/mL of product.

Handling and Dispensing of Cetuximab: Cetuximab must be dispensed only from official study sites by authorized personnel according to local regulations. Cetuximab should be stored in a secure area according to local regulations. It is the responsibility of the Investigator to ensure that study drug is only dispensed to study patients.

Storage Requirement/Stability: Store vials under refrigeration at 2 C to 8 C (36 F to 46 F). DO NOT FREEZE. Increased particulate formation may occur at temperatures at or below 0 C. This product contains no preservatives. Preparations of cetuximab in infusion containers are chemically and physically stable for up to 12 hours at 2 C to 8 C (36 F to 46 F) or up to 8 hours

at controlled room temperature (20 C to 25 C; 68 F to 77 F). Discard any remaining solution in the infusion container after 8 hours at controlled room temperature or after 12 hours at 2 to 8 C. Discard any unused portion of the vial.

Preparation and Administration: Cetuximab must not be administered as an IV push or bolus.

Cetuximab must be administered with the use of a low protein binding 0.2 or 0.22-micrometer in-line filter.

Cetuximab is supplied as a 50-mL, single-use vial containing 100 mg of cetuximab at a concentration of 2 mg/mL in phosphate buffered saline. The solution should be clear and colorless and may contain a small amount of easily visible white amorphous cetuximab particulates. DO NOT SHAKE OR DILUTE.

Cetuximab can be administered via infusion pump or syringe pump.

Infusion Pump:

- Draw up the volume of a vial using a sterile syringe attached to an appropriate needle (a vented spike or other appropriate transfer device may be used).
- Fill cetuximab into a sterile evacuated container or bag such as glass containers, polyolefin bags (eg, Baxter Intravia), ethylene vinyl acetate bags (eg, Baxter Clintec), DEHP plasticized PVC bags (eg, Abbott Lifecare), or PVC bags.
- Repeat procedure until the calculated volume has been put in to the container. Use a new needle for each vial.
- Administer through a low protein binding 0.2 or 0.22-micrometer in-line filter (placed as proximal to the patient as practical).
- Affix the infusion line and prime it with cetuximab before starting the infusion.
- Maximum infusion rate should not exceed 5 mL/min.
- Use 0.9% saline solution to flush line at the end of infusion.

Syringe Pump:

- Draw up the volume of a vial using a sterile syringe attached to an appropriate needle (a vented spike may be used).
- Place the syringe into the syringe driver of a syringe pump and set the rate.
- Administer through a low protein binding 0.2 or 0.22-micrometer in-line filter rated for syringe pump use (placed as proximal to the patient as practical).
- Connect the infusion line and start the infusion after priming the line with cetuximab.
- Repeat procedure until the calculated volume has been infused.
- Use a new needle and filter for each vial.

- Maximum infusion rate should not exceed 5 mL/min.
- Use 0.9% saline solution to flush line at the end of infusion.

Cetuximab should be piggybacked to the patient's infusion line.

Following the cetuximab infusion, a 1-hour observation period is recommended.

Safety Precautions: Appropriate mask, protective clothing, eye protection, gloves, and Class II vertical-laminar-airflow safety cabinets are recommended during preparation and handling. Opened vials must be disposed of at the investigational center as chemotherapy or biohazardous waste provided documented procedures for destruction are in place. Otherwise, opened vials must be returned to BMS for disposal. For questions regarding cetuximab destruction please contact BMS at [name].

Cetuximab therapy should be used with caution in patients with known hypersensitivity to cetuximab, murine proteins, or any component of this product.

It is recommended that patients wear sunscreen and hats and limit sun exposure while receiving cetuximab as sunlight can exacerbate any skin reactions that may occur.

Cetuximab Records at Investigational Site(s): It is the responsibility of the Investigator to ensure that a current record of investigational product disposition is maintained at each study site where investigational product is inventoried and disposed. Records or logs must comply with applicable regulations and guidelines, and should include:

- Amount received and placed in storage area.
- Amount currently in storage area.
- Label ID number or batch number.
- Dates and initials of person responsible for each investigational product inventory entry/movement.
- Amount dispensed to and returned by each patient, including unique patient identifiers.
- Amount transferred to another area for dispensing or storage.
- Non-study disposition (e.g., lost, wasted, broken).
- Amount returned to Sponsor.

BMS will provide forms to facilitate inventory control if the staff at the investigational site does not have an established system that meets these requirements.

Drug Ordering and Accountability: Following submission and approval of the required regulatory documents, a supply of cetuximab may be ordered from BMS. Investigators must complete a Drug Request Form and email it to ([contact]).

Keep in mind that you will need 4-6 vials for weekly maintenance doses, dependent on patient's BSA. Cetuximab is shipped in quantities of 24. Allow 5 business days for shipment of drug from BMS receipt of the C225 (Cetuximab) Clinical Supply Shipment Request form. Drug is protocol specific, but not patient specific.

All product will be shipped via Federal Express in a temperature-controlled container. Shipments will be made from BMS on Monday through Thursday for delivery onsite Tuesday through Friday. There will be no weekend or holiday delivery of drugs. Please contact BMS at [contact] if you have questions or cannot send the form electronically.

It is possible that sites may have more than one cetuximab clinical study ongoing at the same time. It is imperative that only product designated for this protocol number be utilized for this study. To help segregate product for this study from other investigational or marketed product, stickers bearing the protocol number will be provided and should be affixed to the front of the outer carton just above the company names so as not to obscure any marking.

Inside each shipping container, a disposable electronic unit (TagAlertTM) to ensure the product has remained at the appropriate temperature during shipping may be included. This unit may be attached to an information card. The LCD display will show "OK" (indicating no alarm has been triggered) or a black bar and the number(s) 1-4 (indicating an alarm/alarms have been triggered). Should an alarm be triggered, follow the instructions on the attached information card. Display results should be recorded on the packing list. For questions regarding drug requisitioning or shipment contact Bristol-Myers Squibb at [contact].

Important Reorder Instructions: Reorders should be emailed directly to BMS using [contact] for shipment within 5 days. When assessing need for resupply, institutions should keep in mind the number of vials used per treatment dose (~4-6 for weekly doses, dependent on patient's BSA), and that shipments may take 5 business days from BMS receipt of request. Cetuximab is shipped in quantities of 24. Drug is not patient specific. Be sure to check with your pharmacy regarding existing investigational stock to assure optimal use of drug on hand.

Receipt of Drug Shipment: Study drug shipments may include a TagAlertTM unit and attached information card (see above for description) and a clinical supply packing list (CSPL). If included, the pharmacist/study personnel responsible for the clinical study product will need to indicate the condition of the shipment, record the TagAlertTM results, and sign the CSPL in the designated areas. The pharmacist/study personnel will keep a photocopy for the site's records, and return the original to BMS, using the enclosed, pre-addressed envelope. The TagAlertTM unit can be discarded after the reading is recorded on the CSPL.

Drug Destruction and Return: At the end of an infusion for an individual patient, any remaining study drug should be destroyed at the site according to the institution's policy for drug destruction. At the completion of the study, all unused study drugs will also be destroyed at the site as per institutional policy for drug destruction. Please maintain appropriate records of the disposal, including dates and quantities. If approved procedures are not in place, please contact Bristol-Myers Squibb at [contact] for assistance.

Drug Inventory Records: It is the responsibility of the Investigator to ensure that a current record of study drug disposition is maintained at each study site where the study drug is inventoried and disposed. Records or logs must comply with applicable regulations and guidelines.

5.2 IRINOTECAN

Route of administration: Intravenous Supplier: Commercially available Formulation: 100 mg single use vial (20 mg/ml; 5 ml vials)

Storage: Store vials at room temperature. Do not freeze.

Stability: Refrigerated – infusions prepared in D_5W are stable for 48 hours. Room temperature – infusions prepared in D_5W are stable for 24 hours.

[figure not shown]
Preparation: Investigators should use the approved package insert for complete preparation and administration information.

- Must be diluted prior to infusion in Dextrose in D5W. Solutions prepared in Sodium Chloride 0.9% should not be refrigerated.
- Final concentration range from 0.12 to 2.8 mg/ml.

6.0 CRITERIA FOR SUBJECT ELIGIBILITY

6.1 SUBJECT INCLUSION CRITERIA

- Patients must have either (1) histologic proof of a high-grade astrocytoma reviewed by a POETIC institutional pathologist or (2) a radiological diagnosis via MRI scan of a typical diffuse pontine tumor made by a POETIC institutional neuroradiologist. Patients with a radiological diagnosis via MRI scan of a typical diffuse pontine tumor will be enrolled on the diffuse pontine tumor arm of the study regardless of histology in cases that are biopsied. Note: For collaborating non-POETIC institutions, the reviews may be done by an institutional pathologist/neuroradiologist.
- Patients must begin study prescribed therapy within 42 days of neurosurgical resection or biopsy of the tumor (high-grade astrocytoma patients) or radiological diagnosis (diffuse pontine tumor patients).
- Age \geq 3-years and < 22-years-old.
- Brain MRI (and any other studies done according to clinical indications) must not show any definitive evidence of leptomeningeal or extra-neural metastases.

• Patients must have adequate hematopoietic function as defined by:

ANC \geq 1000/µL and platelet count \geq 100,000/µL

• Patients must have adequate organ function as defined by:

Hepatic: total bilirubin < 1.5 mg/dl, AST $\leq 2.5 \text{ x}$ the upper limit of normal.

Renal: serum creatinine ≤ 1.5 x the upper limit of normal for age, or calculated creatinine clearance or nuclear GFR ≥ 70 ml/min/1.73 m².

- Performance status ≥ 50 (Lansky for children ≤ 16 years of age, Karnofsky for patients > 16 years of age). Both performance scales are available in Appendix 1.
- The patient, or for minors, a parent or legal guardian, must give informed written consent indicating they are aware of the investigational nature of this study.

6.2 SUBJECT EXCLUSION CRITERIA

- Evidence of leptomeningeal or extra-neural metastatic disease.
- Prior radiation therapy or chemotherapy
- Pregnancy, mothers unwilling to refrain from breast-feeding, and sexually mature patients unwilling to practice an effective form of birth control
- Other significant concomitant medical illnesses that would compromise the patient's ability to receive all prescribed study therapy.
- Prior therapy which specifically and directly targets the EGFR pathway.
- Prior severe infusion reaction to a monoclonal antibody.
- Significant history of uncontrolled cardiac disease; i.e., uncontrolled hypertension, unstable angina, recent myocardial infarction (within prior 6 months), uncontrolled congestive heart failure, and cardiomyopathy with decreased ejection fraction.
- Patients with known Gilbert's Syndrome.

7.0 RECRUITMENT PLAN

Patients will be offered the opportunity to participate in this trial if they meet all eligibility criteria. There will be no discrimination against females or minorities. Informed consent will be obtained from the patient, or if they are non-emancipated minors, their parent or legal guardian. Consent will be obtained by an investigator authorized to obtain consent. Patients will not receive any payment for their participation in this study.

7.1 Patients or their parent/legal guardian will be required to sign a statement of informed consent indicating the investigational nature of this study.

7.2 The investigators listed on the cover page and their qualified designees at each institution as listed on the FDA 1572 for this study may obtain consent and care for the patients according to good clinical practice and protocol guidelines.

7.3 One to three copies of the informed consent will be signed and dated by the patient, parent or the patient's legally authorized representative and by the physician obtaining informed consent, as per institutional guidelines. If institutional guidelines mandate that only one original copy is signed, the following sentences will refer to photocopies of the original. One copy will be given to the patient/parent/legal guardian to be retained for their personal records. One copy will be maintained on file at the Data and Coordinating Center. The third copy will be confidentially maintained by the participating institution.

7.4 A note will be placed in the medical record documenting that informed consent was obtained for this study, and that the patient and/or his/her parents, to the degree of their understanding, acknowledge and accept the risk of participation in this study.

7.5 Written consent must be documented on the appropriate consent form approved by the Institutional Review Board at the respective POETIC center. Attainment of the written consent must be verified by the Data and Coordinating Center (or equivalent entity) of the participating institution prior to entry on study. A copy of the consent form, along with the eligibility checklist, and Health Insurance Portability and Accountability Agreement (HIPAA) must be submitted to the Clinical Trials Office at the Data and Coordinating Center prior to enrollment of any subject on this study. Verification of subject enrollment on this study will be sent by FAX or email the participating center immediately on receipt of the required documents.

Every effort will be made to include women, children of both sexes and minorities in the study population for this trial. No patient will be excluded from participation in this trial on the basis of gender, ethnicity, or race. Review of accrual to past pediatric multicenter studies of new agents demonstrates the accrual of both genders and all NIH-identified ethnicities to such studies. The small number of patients entered into this trial will obviate any analysis of variation in toxicity profile or response rate with gender or ethnicity.

Data from the institutions participating in this trial have been reviewed with respect to enrollment of patients of different races and genders. It is anticipated that enrollment of the current study will follow the same pattern.

Institution	Number of	White	Black	Hispanic	Other
Institution	Patients	Non-Hispanic	Non-Hispanic	(%)	(%)

		(%)	(%)		
MSKCC	147	61.0	19.0	15.0	5.0
UAHSC	40	35.0	3.0	53.0	9.0
JHMC	77	73.0	21.0	1.0	5.0
UCHSC	154	75.0	0.0	20.0	5.0
MDACC	146	60.0	5.0	29.0	6.0
VMC	116	83.0	15.0	1.0	1.0
UF	93	81.5	16.5	0.8	0.8
РСН	137	65.7	< 0.1	27.7	6.5
СНОА	276	60.5	27.2	9.4	2.9

8.0 **PRETREATMENT EVALUATION**

- Review of the pathology by a POETIC institutional pathologist (not required for patients with unbiopsied diffuse pontine tumors) Note: For collaborating non-POETIC institutions, the review may be done by an institutional pathologist
- Pre-operative brain MRI with/without contrast
- Post-operative brain MRI with/without contrast (high-grade astrocytoma patients only)
- Complete blood count
- Liver function tests: Total bilirubin, AST
- Renal function tests: Creatinine (Creatinine clearance or nuclear GFR study if serum creatinine > 1.5 x upper limit of normal for age)
- For females of child-bearing potential: Urine or serum pregnancy test according to local institutional standards
- All of these pre-treatment evaluations (other than pathology review, pregnancy testing, and the pre-operative brain MRI with/without contrast) must be performed \leq 30 days before registration onto study. Pregnancy testing must be performed \leq 14 days before registration.
- Physical exam

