10.0 EVALUATION DURING TREATMENT/INTERVENTION

The mandated observations are summarized in Appendix 2.

During the first phase of therapy (Radiation therapy with cetuximab)

Physical exams will be performed and potassium, calcium, and magnesium levels will be obtained once a week, prior to each cetuximab infusion.

CBC and other laboratory work will be obtained as clinically indicated.

[figure not shown]
During the second phase of therapy (irinotecan with cetuximab)

Physical exams will be performed and a CBC, potassium, calcium, magnesium, total bilirubin, AST, and creatinine will be obtained prior to each cycle. Laboratory work during a cycle will be obtained as clinically indicated.

Assessment of tumor status via brain MRI will be performed about 3 weeks after completing RT (pre-cycle 1 chemotherapy), then during every 3^{rd} cycle of irinotecan-cetuximab (during cycles 3, 6, and 9).

Following completion of therapy

For patients who complete protocol therapy and remain on study progression-free, MRI scans of the brain will be performed at about 3, 6, 9, 12, 18, 24, 30, 36, and 42 months post-completion of therapy or until the patient has been removed from the study. Subsequent scans will be performed at the clinician's discretion and are not mandated by this protocol, but are recommended approximately annually.

Mandated evaluations including lab work and MRI scans may be performed at other (non-POETIC) centers if deemed clinically indicated as long as they are submitted to the POETIC investigator in a timely fashion.

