15.0 RESEARCH PARTICIPANT REGISTRATION AND RANDOMIZATION PROCEDURES

15.1 RESEARCH PARTICIPANT REGISTRATION

All patients must be centrally registered by the Data and Coordinating Center, at Memorial Sloan-Kettering Cancer Center. Registrations will be handled by the RSA at the Pediatrics Clinical Trials Office at MSKCC. The contact telephone number is [contact] or [contact] and the fax number is [contact]. Registrations will occur between 9:00 am and 5:00 pm Eastern Standard Time (EST), Monday through Friday and will include review of the signed consent form, HIPAA research authorization form, eligibility checklist, eligibility source documentation and Patient Enrollment form. The RSA will also verify, via a FAX copy, that the written informed consent is obtained and dated prior to subject entry on the study.

The participating sites must contact the Research Study Assistant (RSA) at the Data and Coordinating Center to reserve a slot on the protocol when a patient is being considered for a trial. To begin a registration the participating site must fax the signed consent form and HIPAA research authorization to the RSA within 48 hours of the patient signing consent. To complete the registration, the completed eligibility checklist, patient eligibility source documentation and the Patient Enrollment form must be faxed to the RSA at MSKCC prior to protocol treatment or any research tests. Registrations must be faxed to the Clinical Trials Office and the Research Study Assistant (RSA) at MSKCC will verify eligibility and complete the registration with the PPR Office.

Once eligibility has been established and the participant is registered, the participant will be assigned an MSKCC Clinical Research Database (CRDB) number (protocol participant number). This number is unique to the participant and must be written on all data and correspondence for the participant. This protocol participant number will be relayed back to study staff at the registering site via e-mail and will serve as the enrollment confirmation. The participating site must not begin treatment until receiving this email from the Data and Coordinating Center.

Written consent must be documented on the appropriate consent form and Research Authorization designated and approved by the Institutional Review Board at the institution at which the patient is enrolled. The POETIC Principal Investigators or consenting professionals at their institution

The registration procedure is summarized below.

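### The pregnancy-test and laboratory windows are counted back from registration, so a patient who meets every rule can start radiation and cetuximab on tests 42 days old, beyond the protocol's own 14- and 30-day limits

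*Combined protocol and SAP*

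**What the plan says.** Section 8.0 lists the pretreatment evaluations and gives two windows, both measured from registration. For the blood count, total bilirubin, AST and creatinine, the tests "must be performed \leq 30 days before registration onto study". For females of child-bearing potential, "Pregnancy testing must be performed \leq 14 days before registration".

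The start of treatment is governed elsewhere. Section 6.1 says "Patients must begin study prescribed therapy within 42 days of neurosurgical resection or biopsy of the tumor", and sets the same 42 days from radiological diagnosis for pontine patients. Section 15.1 fixes an order of events: "The participating site must not begin treatment until receiving this email from the Data and Coordinating Center". It gives no maximum interval after that email.

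The criteria that these tests serve are in section 6.1 (neutrophils, platelets, bilirubin, AST, renal function) and section 6.2, which excludes "Pregnancy, mothers unwilling to refrain from breast-feeding, and sexually mature patients unwilling to practice an effective form of birth control".

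For the radiation-cetuximab phase, section 10.0 requires a weekly physical exam with potassium, calcium and magnesium before each cetuximab infusion. Beyond that, "CBC and other laboratory work will be obtained as clinically indicated". Section 9.1 adds no laboratory condition for starting. Section 9.2, by contrast, makes the start of the irinotecan-cetuximab phase conditional on neutrophil, platelet and bilirubin values.

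**The concern.** The pregnancy exclusion and the organ-function thresholds protect a patient at the moment treatment begins. A window anchored to registration shows that the patient qualified when the paperwork was completed, and treatment can follow some weeks later. If nothing refreshes the tests in between, someone can satisfy every written criterion and yet be pregnant, or below a threshold, when radiation and cetuximab start.

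The pregnancy test matters most. Eligibility runs from 3 to under 22 years, so the trial can enroll females of child-bearing potential. Section 3.6 states that this combination has not been investigated in pediatric patients. The birth-control condition in section 6.2 lowers the risk between test and treatment but cannot detect a pregnancy. The second phase has a laboratory check at its start and the first phase shows none.

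**Working it through.** The plan states no maximum test age at first treatment, so there is no figure of its own to reproduce. The check is interval arithmetic.

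**Inputs**
- W, the window before registration: 14 days for the pregnancy test, 30 days for blood count, liver and renal tests (section 8.0).
- Latest start: day 42, where day 0 is surgery or biopsy, or radiological diagnosis (section 6.1).
- R, the day of registration. Section 15.1 requires only that R precede treatment. A pontine patient needs "a radiological diagnosis via MRI scan of a typical diffuse pontine tumor made by a POETIC institutional neuroradiologist", so R can be as early as day 0. A high-grade patient needs "histologic proof of a high-grade astrocytoma reviewed by a POETIC institutional pathologist", so R comes after surgery by a pathology turnaround that the documents do not give.

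**Case 1: no test pre-dates diagnosis or surgery.** Test age at first treatment = start day − test day. With the test on day 0 and the start on day 42, age = 42 − 0 = 42 days. Registration on or before day 14 satisfies both windows.
- Pregnancy test: 42 days against 14, an excess of 28 days and 42/14 = 3 times the stated limit.
- Blood tests: 42 days against 30, an excess of 12 days.

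With tests on day 0, any start after day 14 takes the pregnancy test past its window, and any start after day 30 does the same for the blood tests.

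**Case 2: tests may pre-date diagnosis or surgery.** Maximum age = W + (42 − R). The values of R below are assumptions chosen to show the range.

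| Registration day R | Pregnancy test, 14 + 42 − R | Blood tests, 30 + 42 − R |
|---|---|---|
| 0 | 56 | 72 |
| 3 | 53 | 69 |
| 7 | 49 | 65 |
| 14 | 42 | 58 |
| 28 | 28 | 44 |
| 42 | 14 | 30 |

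The top row requires a pregnancy test 14 days before diagnosis and blood tests 30 days before it, registration on the day of diagnosis, and treatment on the last permitted day. The bottom row shows that the windows hold at treatment only when registration and first treatment fall on the same day.

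**Does anything later close the gap?** The tests that section 10.0 mandates in the first phase (physical exam, potassium, calcium, magnesium) do not include those at issue. Sections 8.0 to 10.0 show no repeat pregnancy test. The threshold check in section 9.2 and the pre-cycle laboratory work in section 10.0 apply only from the second phase.

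**The case against.** Anchoring eligibility tests to registration is coherent, because eligibility is verified centrally at that point (section 15.1). No two sections contradict each other and no stated figure is wrong. Clinicians may repeat tests when indicated, and patients who start within days of registration are hardly affected. All of that stands. It makes this an improvement to the rule and limits how many patients it reaches.

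A reader might infer three stronger things that the documents do not support.

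- **That the gap is unlimited, or that 56 and 72 days describe real patients.** The 42-day rule limits the gap indirectly. A test taken on or after the day of diagnosis or surgery can never be more than 42 days old at first treatment. The larger figures depend on tests taken before the tumor was diagnosed or resected, which is permitted but unlikely; section 3.1 describes a usually short history in pontine patients.
- **That the safety objective for radiation with cetuximab is compromised.** The stopping rule in section 14.2 counts only non-hematological toxicity of grade 4 or higher that fails to resolve within 7 days, and it leaves out electrolyte abnormalities. An old neutrophil or platelet count does not enter it. Electrolytes and a physical exam are required before each cetuximab infusion, and section 16.0 calls for toxicity at baseline to be recorded.
- **That the gap is certain across the whole protocol.** Appendix 2 is listed but its table was not available for this review. Section 8.0 ends by calling it a summary of these same evaluations, so a tighter entry there is possible but not indicated.

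**Conclusion.** The point holds as a gap in patient safety and eligibility timing. Under the rules as written, a patient whose tests were all done on the day of diagnosis can start treatment with a pregnancy test and blood tests 42 days old, which is 28 and 12 days beyond the protocol's own windows. The ceilings of 56 and 72 days are theoretical.

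This assumes that Appendix 2 contains no start-of-treatment test. How many patients would be affected cannot be estimated, because the documents give no distribution of the time from registration to treatment.

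The case is strongest for the pregnancy test. It is weaker for the blood tests, where the excess is smaller and clinically indicated testing is at least provided for. The decision rules and error rates for one-year progression-free survival in sections 14.1.1 and 14.1.2 are not affected.

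**What to change.** In section 8.0, keep the sponsor's 14 and 30 days but count them back from the first protocol treatment, with results still available before registration. Add that any pregnancy or laboratory test outside its window on the day of first treatment is to be repeated before treatment begins. Wording along these lines would do: *The pregnancy test must fall within 14 days, and the blood count, bilirubin, AST and creatinine within 30 days, of the first protocol treatment. All must be available at registration, and any that has lapsed by first treatment is repeated.*

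Align the eligibility checklist and Appendix 2 with this text, after checking whether Appendix 2 already carries such an entry. How a repeat result is acted on is for the sponsor to state.

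The cost is a sentence or two of text and a checklist entry, plus a routine blood draw or a urine or serum pregnancy test for the minority whose start falls outside a window. Sample size, decision rules and the primary analysis stay as they are.
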